9.6.3. Log Review

Programmers will review all SAS log files. This procedure is a widely accepted, basic level of program validation. The following issues must be addressed as part of a log review:

- No errors should appear in a log file.
- If warning messages or messages related to uninitialized variables are permitted in the log file, the programmer will document why they are permitted.
- The programmer will account for the number of observations reported at each executed data step, especially when the number of observations increases or decreases.
- The log file will contain all lines of the program as it was saved at the time of execution, and it will contain only those lines of code.

9.6.4. Review of Data Listings and Tables of Summary Statistics

Because an error-free log file does not necessarily demonstrate that a SAS program has functioned as intended, programmers will produce cell frequencies, means, and other summary statistics on specific data items to demonstrate that the program results are valid. Where appropriate, we also will have a separate analyst review these listings independent of the programmer.

9.6.5. Independent Programming

For highly complex programming tasks, a second programmer will attempt (if necessary) to independently reproduce output generated by the initial programmer. If the outputs are equivalent, the test will be considered successful. If the outputs are not equivalent, the programmers will evaluate the differences and make appropriate corrections.

9.6.6. Validation Documentation

For each SAS program used to produce final study outputs for presentation, RTI-HS will complete and store a formal SAS validation document.

9.6.7. Data-collection Form

As used in this protocol, the term DCF should be understood to either a paper form or an electronic data record or both, depending on the data-collection method used in this study.

A DCF is required and should be completed for each included patient. The completed original DCFs are the sole property of Pfizer and should not be made available in any form to third parties, except for authorized representatives (ie, RTI-HS) of Pfizer or appropriate regulatory authorities, without written permission from Pfizer. The investigator shall ensure that the DCFs are securely stored at the study site *in* encrypted electronic form and will be password protected or secured in a locked room to prevent access by unauthorized third parties.

The investigator has ultimate responsibility for the collection and reporting of all clinical, safety, and laboratory data entered on the DCF and any other data-collection forms (source documents) and ensuring that they are accurate, authentic/original, attributable, complete, consistent, legible, timely (contemporaneous), enduring, and available when required.

The source documents are the patient medical records; data collected on the DCFs must match those records.

9.6.8. Record Retention

To enable evaluations and/or inspections/audits from regulatory authorities or Pfizer, the investigator agrees to keep records, including the identity of all participating patients (sufficient information to link records, eg, DCFs and hospital records), copies of all DCFs, safety reporting forms, source documents, detailed records of treatment disposition, and adequate documentation of relevant correspondence (eg, letters, meeting minutes, and telephone call reports). The records should be retained by the investigator according to local regulations or as specified in the study agreement, whichever is longer. The investigator must ensure that the records continue to be stored securely for so long as they are retained.

If the investigator becomes unable for any reason to continue to retain study records for the required period (eg, retirement, relocation), Pfizer should be prospectively notified. The study records must be transferred to a designee acceptable to Pfizer, such as another investigator, another institution, or to an independent third party arranged by Pfizer.

Study records must be kept for a minimum of 3 years after completion or discontinuation of the study, as expressed in separate contractual agreements between Duke University, RTI-HS, and Pfizer.

The investigator must obtain Pfizer's written permission before disposing of any records, even if retention requirements have been met.

RTI-HS and Duke will store in a secure location all copies of the original data files, as applicable. Data files stored on CD, DVD, or other media will be kept in a locked storage unit. Original data files will be housed on dedicated project space on RTI-HS' Linux server.

To ensure the integrity of the original files, they will be stored on the Linux server in a designated folder that cannot be overwritten. Data sets derived from the original files during the data-cleaning process will be stored in a separate folder.

9.7. Data Analysis

All variables described in [Section 9.3](#) will be summarized descriptively through the tabular display of mean values, 95% confidence intervals (CIs), medians, quartiles, and standard deviations of continuous variables of interest and frequency distributions for categorical variables. All open-ended text fields associated with the “other” answer option will be evaluated and described, as appropriate.

All study-eligible patients will be included in descriptive analyses of variables pertaining to patient characteristics, baseline clinical characteristics, and initial postoperative follow-up visits (see [Sections 9.3.1](#), [9.3.2](#), and [9.3.3](#) for details). Patients who are categorized as having a high risk of recurrence will be included in additional analyses described below. Risk classification will be assessed using published algorithms (eg, UISS and SSIGN score) or adaptation of a published algorithm. The primary risk classification system used to designate the high-risk subgroup for this study will be chosen based on completeness of data available in the patient medical records. Completeness will be assessed during the pilot study. If data are available to support more than one classification system, the UISS risk classification will be used. If some data are not available to support classification using a published algorithm, an adapted version of an algorithm will be explored.

Additional descriptive analyses performed within the high-risk subgroup will include referral patterns, treatment patterns, and health outcomes (see [Sections 9.3.4](#), [9.3.5](#), [9.3.6](#)). In addition to descriptive analyses, time-to-event measures (ie, time to recurrence, overall survival) will be assessed. To adjust time-to-event measures, a Kaplan-Meier method that accounts for right-censoring will be implemented (Klein and Moeschberger, 2005).⁷ To evaluate time to recurrence, the endpoint will be programmed with the date of recurrence or date of death, whichever occurs first, as an eligible event; if neither of these events occurred, the outcome will be right censored at the date of the last medical record follow-up. To evaluate overall survival, the endpoint will be programmed with the date of death as an eligible event or right censored at the date of the last medical record follow-up.

Exploratory semiparametric Cox proportional hazards models will be used to evaluate factors associated with time to recurrence and overall survival. These outcomes will be defined as described previously. Separate models will be estimated for time to recurrence and overall survival. The models will take the following general form:

$$h(t) = h_0(t) \exp(\beta_1 \text{DEMOGRAPHIC}_i + \beta_2 \text{CLINICAL}_i), \text{ (Equation 2)}$$

Where the following apply:

- $h(t)$ will be the hazard function of recurrence and overall survival as a function of explanatory variables.

- $h_0(t)$ will be the baseline hazard of recurrence and overall survival.
- DEMOGRAPHIC will be a vector of patient demographic characteristics, including but not limited to the following:
 - Age;
 - Sex.
- CLINICAL will be a vector of underlying clinical characteristics, including but not limited to the following:
 - Tumor histology;
 - Type and duration of systemic treatment;
 - Referral status;
 - Subsequent procedures.

The independent variables included in the final Cox proportional hazard models will be selected through an iterative process. First, separate univariate models assessing the relationship between each potential independent variable (eg, tumor histology) and the time-to-event outcome (ie, recurrence and overall survival) will be fit (Klein and Moeschberger, 2005).⁷ The model with the lowest Akaike information criteria (AIC) will be selected for further evaluation. Next, each unselected variable will be added independently to the previously selected model to determine whether the addition of the specific variable results in a lower AIC. The model with the lowest AIC will be selected for further evaluation. This process will be repeated with each of the remaining unselected variables until the addition of unselected variables no longer lowers the AIC. The most parsimonious model will have the lowest AIC. Additionally, variables of clinical significance may be included in the model. The overall goodness-of-fit of the final model will be assessed using Cox-Snell residuals and the proportional hazards assumption for the final set of covariates (Klein and Moeschberger, 2005).⁷

Cox proportional hazards models will generate a hazard ratio for each of the covariates included in the model, indicating the higher or lower rate of an event (relative to a reference category) at any given point in time following nephrectomy. Like odds ratios from a logistic model, a hazard ratio less than 1 indicates a lower rate of an event, while a ratio greater than 1 indicates a higher rate of an event, relative to a reference category.

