8. RESEARCH QUESTION AND OBJECTIVES

The aim of this study is to estimate the proportion of patients diagnosed with RCC who are at high risk for recurrence following nephrectomy, describe referral patterns, and characterize treatment in this population. Exploratory analyses may include estimation of the incidence of recurrence and disease-free interval following nephrectomy, if data are available. Data for this study will be collected from a retrospective medical record review of patients diagnosed with locoregional RCC who underwent nephrectomy at Duke. The following primary objectives will be assessed:

- Describe patient demographic and clinical characteristics of patients diagnosed with locoregional RCC who underwent nephrectomy.
- Estimate the proportion of patients at high risk of recurrence following nephrectomy.

- Characterize postoperative provider referrals among patients at high risk of recurrence, including the proportion of patients who were referred to other providers and reasons for referral.
- Describe treatment characteristics following nephrectomy among patients at high risk of recurrence, including the proportion of patients who received systemic therapy, type of systemic therapy received, dose and duration of treatment, reasons for treatment discontinuation, and participation in clinical trials, where available; perform subgroup analyses to describe treatment details among the subgroup of patients receiving adjuvant systemic therapy with sunitinib.
- Estimate the incidence of disease recurrence and duration of the disease-free interval following nephrectomy among all patients at high risk of recurrence, and among the subgroup of patients receiving adjuvant systemic therapy with sunitinib.

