9.1.3. Part 3: Expanded Data Collection

Results from the part 2 study indicated that referral and treatment patterns show an increasing trend from 2018 into 2019. To further capture this trend, an additional sample of all patients with nephrectomies occurring through 31 December 2019 will be abstracted. The additional sample size during this period is estimated to be approximately 115-150 patients, for a full

combined sample of up to 650 patients in total. In addition, expanded follow-up data (ie, referral patterns, treatment patterns, and outcomes) will be collected for previously identified patients at high risk of recurrence, to include follow-up dates through the most recent available medical record entry prior to the abstraction date.

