9.2. Setting

Data will be abstracted from the Duke EMR system. Patients whose data will be included in the study will have met the criteria described in [Sections 9.2.1](#) and 9.2.2. Refer to [Figure 1](#) for a depiction of the follow-up period. No minimum follow-up time will be required. Outcomes among patients who are determined to be at high risk of recurrence will be observed over each patient's follow-up period—from the date of nephrectomy to death, disease recurrence, or the last date in their medical record (whichever occurs first).

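### Treatment duration belongs to a primary objective, but Section 9.7 has no rule for courses still running at the last record, so mean duration will be biased downward.

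*Combined protocol and SAP*

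**What the plan says.** Section 8 introduces its list with "The following primary objectives will be assessed". For high-risk patients, one item on that list covers "dose and duration of treatment, reasons for treatment discontinuation, and participation in clinical trials, where available", with treatment details also described for the adjuvant sunitinib subgroup.

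Section 9.7 sets the method for the variables that Section 9.3 lists: they "will be summarized descriptively through the tabular display of mean values, 95% confidence intervals (CIs), medians, quartiles, and standard deviations of continuous variables of interest". Treatment patterns are placed among these descriptive analyses. The section then states: "In addition to descriptive analyses, time-to-event measures (ie, time to recurrence, overall survival) will be assessed". Time to recurrence and overall survival each get an event definition and censoring at the last record. No other duration does.

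Section 9.3.5 collects dates of adjuvant systemic therapy, and Section 9.3.6 collects reasons for discontinuation and the date of the last encounter. Neither section names a treatment stop date or an ongoing-therapy item. Duration is not itself a listed variable and would have to be derived.

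Section 9.2 states "No minimum follow-up time will be required" and ends observation at death, recurrence or the last record. Under Section 9.1.3, "an additional sample of all patients with nephrectomies occurring through 31 December 2019 will be abstracted". Section 6 places that abstraction in Q2 2020.

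**The concern.** A patient still on therapy at the last record has no completed duration. An ordinary mean can leave that patient out, which keeps the courses that ended soon enough to be seen, or it can enter the time so far as if the course had finished. Both understate the mean, and the confidence interval is then centred on a value that is too low. Reasons for discontinuation are affected in the same way: early stops are seen first and are over-represented among the stops observed.

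The calendar makes unfinished courses likely. Surgery is included up to 31 December 2019, abstraction follows within months, and no follow-up is required. At stake is a descriptive result that Section 8 calls primary, including the one for sunitinib.

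**Working it through.** **The plan's own figures.** Section 9.5 expects 98-130 high-risk patients: 650 × 0.15 = 97.5 and 650 × 0.20 = 130, so the figure reproduces. Part 3 adds 115-150 patients (Section 9.1.3). At the same percentages that is 115 × 0.15 = 17.25 to 150 × 0.20 = 30, or about 17-30 high-risk patients. The documents state no treatment duration, number treated or share still on treatment.

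**Time available.** With abstraction between 1 April and 30 June 2020, a nephrectomy on 31 December 2019 has at most 3.0-6.0 months of record, one on 1 April 2019 has 12.0-15.0, and one on 1 April 2014 has 72-75. Time on therapy is shorter, because therapy starts after surgery.

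**Assumptions (not in the documents).** Nephrectomy dates are uniform over the window shown. Therapy starts 1-3 months after surgery. Records are read in mid-May 2020, 4.5 months after 31 December 2019. Stopping is exponential, with a proportion p = 30% or 50% stopping by 12 months. The maximum course C is 12 or 6 months.

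**True mean.** With λ = −ln(1 − p)/12, the mean is (1 − e^(−λC))/λ. For C = 12:
- p = 0.30: λ = 0.0297, mean = 0.30/0.0297 = 10.1 months.
- p = 0.50: λ = 0.0578, mean = 0.50/0.0578 = 8.7 months.

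**Observed means** (simulation; months; C = 12; shortfalls are differences of the rounded means):

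| Nephrectomies | p | Ongoing | True mean | Ongoing dropped (shortfall) | Ongoing counted as complete (shortfall) |
|---|---|---|---|---|---|
| Apr 2014-Dec 2019, even spread | 30% | 11% | 10.1 | 9.9 (0.2) | 9.6 (0.5) |
| Apr 2014-Dec 2019, even spread | 50% | 9% | 8.7 | 8.4 (0.3) | 8.3 (0.4) |
| 2018-2019 only | 30% | 32% | 10.1 | 9.4 (0.7) | 8.6 (1.5) |
| 2018-2019 only | 50% | 26% | 8.7 | 7.8 (0.9) | 7.5 (1.2) |

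With C = 6, about 4% of courses are ongoing over the full window and the shortfall is under 0.1 month. For 2018-2019 it is 0.1-0.2 months.

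**Median.** Over the full window the median is unchanged in three of the four combinations of p and C. In the fourth (p = 50%, C = 12) it falls from 12.0 to 11.1 or 10.0, but there the true median sits exactly at the cap.

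**Second set of assumptions.** Start is fixed at 2 months, exponential stopping has a median of 6 or 9 months, and the course is capped at 12 months. Over the full window 6%-8% of courses are ongoing. Counting them as complete moves the mean from 6.5 to 6.2 and from 7.8 to 7.5, and the median from 6.0 to 5.6 and from 9.0 to 7.9. The Kaplan-Meier median returns 6.0 and 9.0. With an 18-month stopping median the pooled median stays at 12.0, while the mean falls from 9.6 to 9.1.

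**The case against.** The strongest reply is that this is a silence, not a stated choice. Duration is not listed in Section 9.3, so Section 9.7 does not literally prescribe a mean for it. The abstract's time-to-event sentence gives disease-free interval only as an example, which leaves room for other measures. A descriptive table could show ongoing courses on a separate row. The study is descriptive, without formal hypothesis testing, and the objective is limited to available data.

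Most of this is fair as to weight. It does not supply a method: the abstract does not name duration, Section 9.7 names two censored measures and only two, and a separate row for ongoing courses still leaves the mean computed without them.

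A reader might also infer that recent patients will appear to stop earlier than others. For April-December 2019 nephrectomies with a 12-month maximum, the first set of assumptions does leave 67%-81% of courses ongoing, with observed means of 3.7-4.0 or 5.6-6.2 months; the second set leaves 47%-59% ongoing. But no comparison of duration by calendar period is planned, and the figures describe an unstated fraction of about 17-30 high-risk patients. The planned analysis pools all years.

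**Conclusion.** The gap is real and worth closing before the part 3 analysis. If any course is unfinished, the summaries that the plan offers give a mean duration that is too low.

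For the pooled population that the plan analyses, the likely effect is small to moderate: about 0.2-0.5 months with a 12-month maximum course and even spread, and under 0.1 month with a 6-month maximum. It reaches about 0.7-1.5 months (12-month maximum) if treated patients fall in 2018-2019. Section 9.1.3 suggests such clustering, since it reports treatment rising from 2018 into 2019, but does not quantify it. All these figures rest on assumed start times, stopping rates and course lengths.

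Two stronger readings are not supported. The documents do not rule out censoring for duration; they omit it. Nor is the median necessarily understated: it can be unaffected when ongoing courses have already passed it.

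**What to change.** In Section 9.7, add time from first to last dose as a third Kaplan-Meier measure, for all treated high-risk patients and for the sunitinib subgroup, censored at the last record when therapy is ongoing. Report the number ongoing. Tabulate reasons for discontinuation with ongoing at last record as its own category, and show planned completion separately from early stopping.

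In Section 9.3.5, confirm that a stop date or ongoing status is recorded for each course. State how a course is handled when follow-up ends at recurrence or death (Sections 9.1 and 9.2), since observation can close while therapy is still running.

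The cost is a few sentences and one more table, plus a data item if stop date or ongoing status is not already captured. The Kaplan-Meier median may not be reached in small or recent groups; the number ongoing should still be reported there.

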Milestones: Key milestones include finalization of the protocol (December 2018), finalization of the data-collection form (January 2019), completion of ethics submission (January 2019), completion of pilot phase and finalization of feasibility memo (June 2019), start of data collection (July 2019), completion of part 2 data collection (September 2019), completion of part 2 data analysis (November 2019), and finalization of the part 2 study report (December 2019). Additional key milestones relevant to the expanded data collection include finalization of the updated protocol (Q1 2020), completion of ethics submission (Q1 2020), start of expanded data collection (Q2 2020), completion of expanded data collection (Q2 2020), completion of expanded data analysis (Q2 2020), and finalization of the updated study report (Q3 2020).

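### Section 9.7 gives referral and systemic therapy only crude frequencies, with no by-year or censoring-adjusted estimate, so shorter follow-up pulls the newest cohort's percentages down

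*Combined protocol and SAP*

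**What the plan says.** Section 9.1.3 gives the reason for part 3: "Results from the part 2 study indicated that referral and treatment patterns show an increasing trend from 2018 into 2019". It continues: "To further capture this trend, an additional sample of all patients with nephrectomies occurring through 31 December 2019 will be abstracted". The same section extends follow-up of high-risk patients already identified to their latest record entry before abstraction.

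The primary objectives in Section 8 include, for high-risk patients, "the proportion of patients who were referred to other providers and reasons for referral" and "the proportion of patients who received systemic therapy". Change over calendar time is not a listed objective.

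Section 9.7 summarises the Section 9.3 variables, using "frequency distributions for categorical variables" where they are categorical. It then adds that "time-to-event measures (ie, time to recurrence, overall survival) will be assessed", and ties the Kaplan-Meier method to those two outcomes. The abstract is more open (its list is introduced by eg), but the only example it gives is disease-free interval. No section names an analysis by year of nephrectomy, and calendar year is not among the Cox covariates listed in Section 9.7.

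On follow-up, Section 9.2 states: "No minimum follow-up time will be required". The abstract's milestones put the "start of expanded data collection (Q2 2020), completion of expanded data collection (Q2 2020").

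**The concern.** Referral and systemic therapy accrue over time after nephrectomy. A patient operated on in December 2019 and not yet referred when the record is abstracted falls into the no-documented-referral category of Section 9.3.4, exactly like a patient observed for two years without referral. If the trend is read from crude percentages by year, the cohort added to show it is also the cohort with the least time to show it. A real rise could look flat or smaller than it is.

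Section 9.7 already uses a method that handles right-censoring for recurrence and survival. Referral and therapy are observed over the same unequal follow-up and get none. Summarising days to referral as a continuous variable does not fill the gap, because it covers only patients already referred.

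**Working it through.** **The plan's own figure.** Section 9.5 expects 98-130 high-risk patients among about 650: 650 × 0.15 = 97.5, and 650 × 0.20 = 130. This reproduces. Part 3 adds 115-150 patients (Section 9.1.3), hence about 115 × 0.15 = 17 to 150 × 0.20 = 30 high-risk patients.

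**Potential follow-up** (abstraction date minus nephrectomy date, for 1 April to 30 June 2020; month = 30.4375 days):
- 31 December 2019 nephrectomy: 92-182 days (3.0-6.0 months).
- 1 April 2019 nephrectomy: 366-456 days (12.0-15.0 months).
- 2018 nephrectomies: 457-911 days (15.0-29.9 months).

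**Model for the crude percentage.** The documents give no referral timing, so all of these are assumptions: the same eventual proportion p = 40% in every year (no true trend), exponential time to referral with median m among those referred, nephrectomies uniform within the year, and abstraction on 15 May 2020. Follow-up c is then 501-865 days for 2018 and 136-500 days for 2019.

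- No exit before abstraction: expected crude share = p × mean over c of [1 − exp(−λc)], with λ = ln 2 / m.
- Exit at constant rate μ: expected crude share = p × λ/(λ+μ) × mean over c of [1 − exp(−(λ+μ)c)]. For 40% gone by 24 months, μ = −ln(0.6)/24 = 0.0213 per month. For 50% gone by 12 months, μ = ln 2 / 12 = 0.0578 per month.

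| Median m (months) | 2018 v 2019, no exit (%) | Fall, no exit (points) | Fall, 40% gone by 24 months | Fall, 50% gone by 12 months |
|---|---|---|---|---|
| 1 | 40.0 v 39.8 | 0.2 | 0.2 | 0.1 |
| 2 | 40.0 v 38.0 | 2.0 | 1.6 | 1.2 |
| 3 | 39.7 v 35.2 | 4.5 | 3.6 | 2.4 |
| 6 | 36.8 v 27.1 | 9.7 | 7.3 | 4.5 |
| 12 | 28.8 v 17.7 | 11.2 | 8.1 | 4.9 |

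Earlier exits shorten the older cohort's observation more, so for this p and this cut the no-exit column is close to an upper value. Without exit, the falls at the five medians are 0.6, 3.3, 6.3, 11.5 and 12.1 points for a 1 April cut, and 0.1, 1.2, 3.2, 8.2 and 10.2 for a 30 June cut. The fall is proportional to p.

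**Pooled proportions** (the Section 8 objectives). I weighted 75-100 part 2 patients, uniform over April 2014 to March 2019, with 17-30 part 3 patients, at p = 40%, mid-May, no exit. The shortfall from the eventual 40% is under 0.1, 0.4-0.8, 1.0-1.8, 3.2-5.1 and 7.9-10.6 points at the five medians. Each is smaller than the corresponding no-exit fall.

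**Sampling error.** Spread part 2's 75-100 high-risk patients evenly over five years. Then 2018 has 75/5 = 15 to 100/5 = 20, and 2019 has 17 + 75/20 = 20.75 to 30 + 100/20 = 35. The half-width is 1.96 × √[0.4 × 0.6 × (1/n₁ + 1/n₂)]: 32.5 points for 15 v 20.75 and 26.9 points for 20 v 35.

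**Reach of a 90-day estimate.** The shortest potential follow-up is 92 days, so 90 days lies within potential follow-up for every cohort. The share of eventual referrals captured is 1 − 2^(−90/m), with m in days: about 87%, 64%, 50%, 29% and 16% at the five medians.

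**The case against.** The strongest reply has four parts.

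- **The harm is doubly conditional.** Trend is not an objective in Section 8, and nothing says it will be read from crude percentages. That stands. But trend is the stated reason for part 3, and the affected proportions are objectives.
- **Noise exceeds the bias.** It does in every scenario tried, and at a 6-month median with 40% eventually referred a 90-day estimate would rest on only about 2.0-3.5 events in 17-30 patients. That also stands and limits the weight of the point. Still, an interval shows sampling error to the reader, whereas a crude percentage does not show truncation.
- **Timing may be early.** At a 1-month median the bias is negligible. Day-interval summaries under Section 9.7 would give some indication, though only among patients already referred. A cumulative incidence curve would show the timing properly.
- **Part 2 faced the same handicap and still reported a rise.** For part 2 collection around 8 August 2019, the no-exit model at 40% gives a downward gap between 2018 and January-March 2019 of about 1, 5, 8, 11 and 10 points at the five medians. This makes the longest medians less likely, without settling the timing.

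A reader might infer that the reported rise is an artefact of follow-up. The documents do not support that, because the mechanism runs the other way. Nor do they support the inference that a by-year analysis is impossible: part 2 evidently produced calendar-time results, and Section 10 keeps year of nephrectomy in the analytic file. It is simply not specified.

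**Conclusion.** The point holds as a low-severity improvement to a descriptive, exploratory study. The gap in Section 9.7 is textual, and the downward direction for the newest cohort follows from the plan's own dates. The size does not follow from the documents. At 40% eventually referred and a mid-May 2020 cut, it runs from negligible with early referral to 11.2 points at a 12-month median without exit, and to 8.1 or 4.9 points under the two assumed exit rates. The effect on the pooled proportions is smaller.

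It is tempting to say that the dates already collected would remove the bias. They would not remove all of it. Censoring at the last record entry assumes that leaving Duke care is non-informative. Yet transfer to a non-Duke provider is a recorded follow-up plan (Section 9.3.3), and outside care absent from the record is unavailable (Section 9.9). Only the part due to unequal follow-up is reduced.

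**What to change.** Add a paragraph to Section 9.7 along these lines: in the high-risk subgroup, time from nephrectomy to first RCC-related referral and to first systemic therapy is summarised by cumulative incidence, with death and recurrence as competing events and censoring at the last medical record entry. Estimates are given with 95% CIs and numbers at risk, overall and by year of nephrectomy, at 90 days for all cohorts and at later times. Results are descriptive.

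Show the follow-up plan from the first postoperative visit (Section 9.3.3) by year beside it. That plan is less exposed to unequal follow-up, but it records an intention rather than a referral or treatment received. Confirm that referral and therapy intervals are among those transferred as days from index under Section 10.

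The cost is a paragraph and a table, because referral and adjuvant-therapy dates are already collected (Sections 9.3.4 and 9.3.5). The downsides are wide by-year intervals, a 90-day figure that misses later events, and the remaining assumption about departure from Duke care, which should be stated with the results.
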